9.6 Bayley Scales of Infant and Toddler Development, Third Edition

Bayley-III scales are completed within the core study (except for EP0065) if the subject is enrolled in an English-speaking country or a country where a validated translation is available, and data should not be recorded in the eCRF in N01266. If not stated otherwise, the EV data from core study will be obtained as EV data for N01266. For LTFU subjects coming from N01349, the Bayley-III data recorded at FV of N01349 will be obtained as EV data for N01266. Subjects that have been rolled-over from core study EP0065 will complete the Bayley-III questionnaire at the EV of N01266. For N01263 LTFU subjects, the Baseline Bayley-III questionnaire data of the core study will be obtained as EV data for N01266. Directly enrolled subjects will not have data of this type as they are enrolled at an older age than the cohort of ≥ 18 to ≤ 42 months covered by this assessment.

The Bayley-III scales will be completed for LTFU subjects at the FEV, YEV, FV, and at the EDV in the case of early discontinuation.

The sum of scaled scores entered on the eCRF, and change from Baseline for the cognitive scale, language composite scale, motor composite scale, and social-emotional scales, as well as the adaptive behavior scale, will be summarized at Baseline and each visit during the Evaluation Period, if available. All recorded raw scores, scaled scores, composite scores, percentile rank and growth scores will be listed.

9.7 PedsQL assessment

The PedsQL is completed at the ScrV (DE subjects only), FEV, YEV, FV, and the EDV in the case of early discontinuation. For LTFU subjects (except those from core studies EP0065,

N01349 and N01263), at the EV, the PedsQL score will be obtained from Baseline of the core study for subjects ≥ 2 years and is not recorded in the eCRF in N01266. For DE subjects the Baseline PedsQL is completed at the ScrV, for LTFU subjects from core study EP0065 the Baseline PedsQL is completed at the EV of N01266. Within core studies N01349 and N01263 PedsQL assessment was not performed. Furthermore, PedsQL assessment was not done at the EV of N01266 for N01263 and N01349 LTFU subjects. Therefore, Baseline PedsQL is not available for those LTFU subjects.

For subjects <5 years of age only parent-report-scores for PedsQL are available, for subjects ≥ 5 years of age self-reporting scores as well as parent-reporting scores for PedsQL might be available. Self-reporting and parent-reporting scores will be summarized separately. Complete score-related data will be listed.

Calculated values and change from Baseline (if available) for the total scale score, psychosocial health score and each of the 4 scale scores will be summarized for each visit during the Evaluation Period where the questionnaire is entered. Subgroup summaries by age will be performed using the age groupings for which different questionnaires are entered; ≥ 2 to ≤ 4 years, ≥ 5 to ≤ 7 years, ≥ 8 to ≤ 12 years, and ≥ 13 to ≤ 18 years.

All PedsQL data will be listed.

10 PHARMACOKINETICS

Pharmacokinetic samples will be taken for determination of BRV plasma concentration on FEV and on FV or EDV. In addition to the scheduled assessments, it should be obtained whenever a subject experience an SAE.

Subjects receiving phenytoin as a concomitant AED during the study will have blood samples collected at the ScrV (DE subjects only), FEV, YEV, FV, or at the EDV in the case of early discontinuation and Safety Visit (SV) to monitor phenytoin plasma concentrations. The PK samples will also be taken for determination of phenytoin plasma concentration, if applicable.

The plasma concentrations data will only be listed.

11 REFERENCES

National Center for Health Statistics in collaboration with the National Center for Chronic Disease Prevention and Health Promotion. 2000. <http://www.cdc.gov/growthcharts> (accessed 23 Dec 2013).

J W Varni The PedsQL: measurement model for the pediatric quality of life inventory
<https://www.pedsql.org/index.html>

This document cannot be used to support any marketing authorization
application and any extensions or variations thereof.
PUBLIC COPY

12 APPENDICES**12.1 PCST Criteria for Hematology and Biochemistry Parameters**

Parameter	Age Range	UNIT	Abnormality Criteria
Hematology			
Hematocrit	<2y	%	≤27 >45
	≥2y - <18y		≤29 >47
Hemoglobin	<2y	g/dL	≤9.0 >15.0
	≥2y - <18y		≤9.5 >16.0
WBC/Leukocytes	<12y	10 ⁹ /L	≤3.5 >15.0
	≥12y		<3.0 >12.0
Lymphocytes	<6m	%	≤30.0
	≥6m - <6y		≤22.0
	≥6y - <18y		≤12.0 ≥80.0
Basophils	>1m	%	≥3.0
Eosinophils	>1m	%	≥10.0
Monocytes	>1m	%	≥20.0
Platelets	>1m	10 ⁹ /L	≤100 >600
RBC/ Erythrocytes	<2y	10 ¹² /L	<3.0
	≥2y		<3.5
Biochemistry			
AST (SGOT)	<14y	U/L	>180
	≥14y		>144
ALT (SGPT)	1y - <18y	U/L	>90
Alkaline Phosphatase	<4y	U/L	>690

Parameter	Age Range	UNIT	Abnormality Criteria
	≥4y - <10y		>834
	≥10y - <17y		>1174
GGT	<6m	U/L	>522
	≥6m - <1y		>279
	≥1y - <13y		>66
	≥13y - <18y		>126
Total Bilirubin	>1m	mg/dL	≥1.5
Total Protein	2m-<1y	g/dL	<3.0 >10.0
	≥1y		<4.3 >10.0
Albumin	<1y	g/dL	<1.6 >6.0
	≥1y		<2.4 >7.0
BUN	<1y	mg/dL	>21
	≥1y		>30
Urea	<1y	mg/dL	>42
	≥1y		>60
Creatinine	1y - <10y	mg/dL	>0.9
	≥10y - <16y		>1.4
Creatinine Clearance ^a	All	mL/min	<70
Calcium	<1y	mg/dL	<6.9 >12.2
	1y - <18y		<7.4 >11.7
Phosphorous	<1y	mg/dL	<1.8 >8.2
	≥1y		<1.8 >7.4
Potassium	<1y	mEq/L	<3.0 >6.5
	≥1y		<3.0 >5.8

Parameter	Age Range	UNIT	Abnormality Criteria
Sodium	>1m	mEq/L	≤130 ≥150
Glucose	>1m	mg/dL	<50 >180
Total Cholesterol	1y - <18y	mg/dL	>250
LDL (calculated)	1y - <18y	mg/dL	>140
HDL	≤2y	mg/dL	<10
	>2y		<20
Triglycerides	<1y	mg/dL	>750
	≥1y		>250
Uric Acid	<1y	mg/dL	>7.7
	1y - <13y		>6.5
	≥13y - <18y		>8.6
Thyroxine (T4)	<1y	ug/dL	≤4.3 ≥18.4
	≥1y		≤3.8 ≥13.5
Globulin	<1y	g/dL	<1.0 ≥3.8
	≥1y		<1.2 ≥4.4

m=month; y=year.

ALT=alanine aminotransferase; AST=aspartate aminotransferase; BUN=blood urea nitrogen; CrCl=creatinine clearance; dL=deciliter; GGT= gamma-glutamyltransferase; HDL=high density lipoprotein; LDL=low density lipoprotein; L=liter; μ g=microgram; m=month (defined as 30 days); mg=milligram; PCST=possibly clinically significant treatment-emergent; U=unit; y=years (defined as 365.25 days)

^aSchwartz equation (subjects <12): CrCl ml/min=[Height (cm) * 0.55] / serum creatinine

Cockcroft equation (subjects ≥12): Male: CrCl ml/min=[(140-age) x body weight (kg)] / (72 x serum creatinine);
Female: CrCl ml/min=[(140-age) x body weight (kg)] / (72 x serum creatinine)] x 0.85

Note: A month is defined as 30 days; a year is defined as 365.25 days.

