2 PROTOCOL SUMMARY

This is a Phase 3, open-label, single-arm, multicenter, long-term study to evaluate the safety and efficacy of brivaracetam (BRV) in children with epilepsy. This study is designed for pediatric subjects ≥ 1 month to <17 years of age who have completed other pediatric BRV studies (herein referred to as “long-term follow-up” [LTFU] subjects) and for at least 100 subjects ≥ 4 years to <17 years of age with partial-onset seizure (POS) who had not previously enrolled in a pediatric BRV study (herein referred to as “directly enrolled (DE) subjects”), with a planned total enrollment of approximately 600 subjects.

The primary objective is to document the long-term safety and tolerability of BRV. The secondary objective is to assess the efficacy of BRV during long-term exposure. The other objectives are to explore direct cost parameters and to assess the effect of BRV 1) on behavior and cognition using the age-appropriate Achenbach Child Behavior Checklist (CBCL/1½-5 or CBCL/6-18) for LTFU subjects ≥ 18 months of age at Baseline of their initial BRV study (herein referred to as their “core study”) and for all DE subjects, 2) on cognition using the Behavior Rating Inventory of Executive Function® (BRIEF®)/BRIEF®-Preschool Version (BRIEF®-P), and 3) on quality of life using the Pediatric Quality of Life Inventory™ (PedsQL™) for LTFU subjects ≥ 2 years of age at the Baseline of the core study and for all DE subjects. The Bayley Scales of Infant and Toddler Development®, Third Edition (Bayley-III®) will be used to assess LTFU subjects enrolled in English-speaking countries and in countries where a validated

translation is available and <18 months of age at Baseline of the core study; the Bayley-III will not be used to assess DE subjects since all are to be ≥ 4 years of age.

The LTFU subjects will enter directly into the Evaluation Period at the Entry Visit (EV) and will continue BRV treatment at the individualized dose they were receiving at the completion of their core study. Directly enrolled subjects will enter N01266 at the Screening Visit (ScrV) and then participate in up to 3 weeks of an Up-Titration Period. If a DE subject demonstrates, in the opinion of the Investigator, acceptable tolerability and seizure control on the same daily dose of BRV (no lower than 1mg/kg/day) for 7 ± 2 days during the Up-Titration Period, the subject will attend the EV and enter the Evaluation Period on that dose.

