2.3.3 Study duration per subject

Subject participation will extend from study entry for at least 3 years until approval of BRV has been obtained for pediatric subjects in their age range, until a managed access program is established as allowed per country-specific requirements in addition to legal and regulatory guidelines, until subjects transition to another BRV study, or until the investigational product development in the related age range of the pediatric population is stopped by the Sponsor, whichever comes first.

Study entry is defined as the EV for LTFU subjects and the ScrV for DE subjects.

The end of the study is defined as the date of the last visit of the last subject in the study.

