8.3 Clinical laboratory evaluations

Clinical laboratory results will be summarized using conventional units. Observed values and change from Baseline values for hematology, biochemistry (including hepatic monitoring of ALT, AST, ALP, total bilirubin, and GGT) and endocrinology parameters will be summarized for Baseline, each scheduled visit in the Evaluation Period, Last Value on Treatment, and the Safety Visit (if available). These summaries will be repeated separately for data collected during the Up-Titration visits for DE subjects.

Presentation of urinalysis results will consider subjects by age group for whom sample collection is feasible due to the constraints on collection for subjects below 4 years of age in the protocol. Following age groups will be presented: ≥ 4 to < 12 years, ≥ 12 years to < 17 years and overall.

In microscopic urinalysis, a small sample of urine is centrifuged to remove the liquid. The sediment is then examined under a microscope. In the urinalysis laboratory test group, other than qualitative responses, a listing of microscopic analysis parameters will be provided; no summaries of microscopic analysis findings are planned.

Response categories are negative, 1+, 2+, and 3+ for the quantitative urinalysis parameters occult blood, leukocytes, glucose, protein, and ketones and negative and positive for nitrates. Outcome values for these parameters are mapped to the levels Negative, 1+, 2+, and 3+ as follows for purposes of summary tables and the determination of PCST:

Table 8-1: Urinalysis categorization

Category	Definition
Negative	“Negative”, “NEGATIVE” or other outcomes that clearly reflect a negative finding
1+	“1+”, “+”, “Trace”, “TRACE” or other outcomes that clearly reflect trace amount
2+	“2+” or “++”
3+	“3+”, “+++” or other outcomes that clearly reflect the data above 3+ (eg, “4+”, “5+” etc.) or more than 4 plus signs (eg, “++++”, “+++++” etc.)

For qualitative urinalysis parameters (occult blood, leukocytes, glucose, protein, ketones, and nitrates), the number and percentage of subjects with each response category will be summarized for Baseline, EV, each scheduled visit during the Evaluation Period for which urinalysis parameters were scheduled to be assessed, Last Value on Treatment, and the Safety Visit. Percentages for each parameter will be relative to the number of subjects with a microscopic urinalysis assessment at each time point. The summary will be repeated for the Up-Titration period for DE subjects.

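### The creatinine clearance equation changes at age 12 under one <70 mL/min limit, so values and PCST-low flags can shift in either direction with no change in serum creatinine.

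*SAP*

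**What the plan says.** The biochemistry part of SAP Appendix 12.1 has a row for "Creatinine Clearance" with a single low limit, <70 mL/min, for all ages. Footnote a gives two derivations. Below 12 years it is 0.55 x height (cm) / serum creatinine, with no weight or sex term. From 12 years it is "Cockcroft equation (subjects ≥12): Male: CrCl ml/min=[(140-age) x body weight (kg)] / (72 x serum creatinine" for boys and "Female: CrCl ml/min=[(140-age) x body weight (kg)] / (72 x serum creatinine)] x 0.85" for girls, with no height term.

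The value can reach two outputs in Section 8.3. One is the by-visit summary, "Observed values and change from Baseline values for hematology, biochemistry". The other is the count of subjects with any post-Baseline PCST value, overall and by age group. Section 3.9 defines a PCST value as one that meets the criterion after the first dose. It does not require a normal Baseline or any change.

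The population makes crossing age 12 possible. Section 2: "This study is designed for pediatric subjects ≥ 1 month to <17 years of age". Section 2.3.3: "Subject participation will extend from study entry for at least 3 years until approval of BRV", with further conditions that can end participation earlier. Under Section 3.3 the laboratory Baseline of an LTFU subject dates from no later than the first BRV dose in the core study. Nothing in the SAP links the two equations, fixes one per subject, or deals with subjects who turn 12 on study.

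**The concern.** A change from Baseline is interpretable only if both values come from the same derivation. Here a child aged 11 at Baseline and 12 at a later visit would have a height-based value subtracted from a weight-based one. The difference then contains a step set by body size and sex, not by the kidney. As the PCST criterion is a plain threshold, that step alone can move a subject across 70 mL/min.

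At stake is the reading of one renal safety parameter in a single-arm study whose primary objective is long-term safety. No control group exists in which the same artefact would show.

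**Working it through.** The SAP prints no worked clearance value, so there is no figure to reproduce. The check puts the same child, with the same creatinine, through both printed equations at age 12.

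**Inputs from the SAP (Appendix 12.1).** Height equation: 0.55 x H / Scr. Weight equation: (140 - age) x W / (72 x Scr), x 0.85 for girls. Limit: <70 mL/min.

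**Assumptions.** The heights, weights and creatinine values are illustrative; the SAP gives none.

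**Ratio at age 12.** 140 - 12 = 128, and creatinine cancels.
- Boys: (128 x W / 72) / (0.55 x H) = 3.232 x W/H
- Girls: 0.85 x 3.232 x W/H = 2.747 x W/H

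The equations agree only at W/H = 1/3.232 = 0.309 kg/cm (boys) and 1/2.747 = 0.364 kg/cm (girls). At 150 cm that is 46.4 kg and 54.6 kg. A lighter child steps down and a heavier child steps up.

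**Size of the step at constant creatinine**

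| Height / weight | Boy | Girl |
|---|---|---|
| 140 cm / 30 kg | -30.7% | -41.1% |
| 145 cm / 35 kg | -22.0% | -33.7% |
| 150 cm / 40 kg | -13.8% | -26.7% |
| 150 cm / 50 kg | +7.7% | -8.4% |
| 155 cm / 60 kg | +25.1% | +6.4% |
| 155 cm / 70 kg | +46.0% | +24.1% |

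**Flag gained.** Girl, 150 cm, 40 kg, 0.9 mg/dL:
- height equation: 0.55 x 150 / 0.9 = 91.7
- weight equation: 128 x 40 x 0.85 / (72 x 0.9) = 67.2, below 70

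**Flag lost.** Boy, 150 cm, 50 kg, 1.2 mg/dL:
- height equation: 0.55 x 150 / 1.2 = 68.8, below 70
- weight equation: 128 x 50 / (72 x 1.2) = 74.1

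**Creatinine range in which the flag changes.** Setting each equation equal to 70:
- Girl, 150 cm, 40 kg: 0.55 x 150 / 70 = 1.18 mg/dL before the switch and 128 x 40 x 0.85 / (72 x 70) = 0.86 after it. Between these values a flag appears.
- Boy, 150 cm, 50 kg: 1.18 before and 128 x 50 / (72 x 70) = 1.27 after. Between these values a flag disappears.

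Outside such a range the value still steps but the flag does not change. The same girl at 0.6 mg/dL goes from 137.5 to 100.7 and is not flagged on either side.

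**The case against.** **Which age applies is not stated.** The footnote says only below 12 and from 12. Where the SAP means age on the date of assessment it can say so, as in the body-weight row of Appendix 12.3, and the age in years programmed in Section 6.1 is a single baseline age. If Baseline age decides the equation, no child switches. This stands as an ambiguity. Age at assessment is the more natural reading, because age is itself a term in the second equation. Under the other reading the break lies between children on either side of 12, which is also a boundary of the reporting age groups in Section 4.8.

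**Reporting is not confirmed.** Section 3.9 restricts PCST criteria to analytes routinely collected under the protocol, which is not at hand, and Section 8.3 does not name creatinine clearance. This stands as a condition on the whole point. The limit and derivation in the appendix suggest that use is intended.

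**Consequences are limited.** Laboratory tests are other variables (Section 2.2.3), all summaries are descriptive (Section 3.1), and the listings will show serum creatinine. This lowers the severity, but the summary tables would still mix the two equations.

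A reader might infer more than the SAP supports:
- *A one-sided false alarm.* Heavier children rise and can lose a flag, and a flag change needs creatinine within a limited range.
- *A large number of affected subjects.* The SAP gives no distribution of age, size or creatinine, and participation can end before three years.
- *A conflict between the <70 limit and the serum creatinine limit of >1.4 mg/dL at 10 to under 16 years, caused by the switch.* The two limits already differ under the height equation, agreeing only at 1.4 x 70 / 0.55 = 178 cm. They are separate parameters, and the fix below is not meant to align them.
- *A wrong unit.* Both equations and the limit are given in mL/min, and nothing in the SAP shows an error.

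**Conclusion.** The point holds in a limited form. Two equations that agree only at one weight-to-height ratio per sex share one limit, and the change between them falls at an age that subjects can pass while on study. Under age at assessment, change from Baseline and PCST-low status can alter at constant creatinine. For the body sizes tried, the step runs from a fall of 41.1% to a rise of 46.0%, so flags can be created or removed. Under Baseline age, the same discontinuity separates children below 12 from those at 12 and over.

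The ratios follow from the printed equations alone. The individual examples rest on assumed sizes and creatinine values. Frequency cannot be computed from the SAP, and the point has practical effect only if creatinine clearance is reported under Section 3.9. It is worth correcting as a derivation rule. It does not touch the primary variables, which are treatment-emergent AEs and SAEs.

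**What to change.** In footnote a to Appendix 12.1:
1. Derive all of a subject's creatinine clearance values, at Baseline and every post-Baseline visit, with one and the same equation, for example the height-based one already printed. Change from Baseline and PCST status then never mix equations.
2. State that age at assessment is used wherever age enters the calculation.
3. If both equations are kept across subjects, present the <70 counts separately by equation.

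Moving the switch to a later age such as 18 would only relocate the break. If creatinine clearance is not to be reported, deleting the row and footnote settles the matter.

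The cost is an appendix edit and one derivation from data already collected: height and body weight are study variables in Section 2.2.3. There is a small downside. Section 3.2.9 names laboratory parameters, vital signs and body weight as assessed at all Evaluation Period visits, but not height. The most recent recorded height may therefore have to be carried to some visits, and in a growing child this understates clearance in proportion to the missed growth.

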12.2 PCST Criteria for Urinalysis

Qualitative urine parameters are generally reported by a descriptive score, which differs among laboratories. For data analysis purpose, a four-point scale is used. Five-point, six-point, or seven-point scales will be collapsed into a four-point scale first. A value is considered possibly clinically significant treatment-emergent abnormal if an upward shift of at least 2 degrees from the Baseline occurs under investigational treatment. To collapse the results in a five-point scale into a four-point scale, the lowest 2 positive results will be combined (see example below).

Conversion of results in a five-point scale into a four-point scale

Original Five-point Scale	Four-point Scale
Negative/None	Negative/None
Trace/Rare/Mild/A Few	Trace/1+/Rare/Mild/A Few
1+	
2+/Mod	2+/Mod
3+/Sev	3+/Sev

The original scale and four-point scale for PCST of each urinalysis parameter is described in the table below.

Urinalysis 4-point scales for PCST criteria

PARAMETER	Negative	1+	2+	3+
Protein	Negative	Trace, 30 mg/dL	100 mg/dL	≥ 300 mg/dL, ≥ 1000 mg/dL
Glucose	Negative	100 mg/dL, 250 mg/dL	500 mg/dL	≥ 1000 mg/dL
Ketones	Negative	Trace, 15 mg/dL	40 mg/dL	≥ 80 mg/dL, ≥ 160 mg/dL
Hemoglobin (Occult blood)	Negative	Trace, Small	Moderate	Large
Leukocyte Esterase	Negative	Trace, Small	Moderate	Large
Erythrocytes or Leukocytes	1-5 6-10	11-20	21-25	>25

For parameters which cannot have negative values their lowest two positive values will be in category “Negative”. For parameters which can have negative values their lowest two positive values will be at category 1+.

12.3 PCST Criteria for Vital Signs

Parameter (Unit)	Age Range	Abnormality criteria
Pulse Rate (beats/minute)	<6m	<100 >180
	$\geq 6m - < 3y$	<90 >150
	$\geq 3y - < 12y$	<60 >130

Parameter (Unit)	Age Range	Abnormality criteria
	$\geq 12y - < 17y$	<50 >120
Systolic Blood Pressure (mmHg)	<6m	<60 >100
	$\geq 6m - < 3y$	<70 >120
	$\geq 3y - < 12y$	<80 >140
	$\geq 12y - < 17y$	<90 >160
Diastolic Blood Pressure (mmHg)	<6m	<40 >65
	$\geq 6m - < 3y$	<45 >75
	$\geq 3y - < 12y$	<50 >80
	$\geq 12y - < 17y$	<50 >105
Body Weight	1m - <17y	<3% or >97% of the normal body weight growth curve ranges based on gender and the age of subject on date of weight assessment
	$\geq 17y$	A decrease/increase from Baseline of $\geq 10\%$

m=month, y=year.

Note: A month is defined as 30 days; a year is defined as 365.25 days.

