BRV (tablet and oral solution) should be administered twice daily (bid) in 2 equally divided doses. All LTFU subjects must be able to tolerate the minimum dose specified in the core study to be eligible for entry into the Evaluation Period of N01266. All DE subjects must be able to tolerate at least 1mg/kg/day during the Up-Titration Period prior to entering the Evaluation Period of N01266.

The maximum allowable BRV dose is 5.0mg/kg/day (2.5mg/kg bid), not to exceed a dose of 200mg/day. Subjects will receive oral solution or tablets, as appropriate. With the exception of dose adjustments for BRV during the Up-Titration Period, which should be made in accordance with the protocol-specified guidelines, dose adjustments of BRV and any concomitant antiepileptic drugs (AEDs) are allowed at any time based on clinical judgment.

Subjects will receive BRV treatment in this study for at least 3 years, until approval of BRV has been obtained for pediatric subjects in their age range, until a managed access program is established as allowed per country-specific requirements in addition to legal and regulatory guidelines, until subjects transition to another BRV study, or until the investigational product development in the related age range of the pediatric population is stopped by the Sponsor, whichever comes first.

For LTFU subjects, the EV is the first study visit. For DE subjects, the EV occurs after subjects have completed the ScrV and at least 1 Titration Visit (TV), and have maintained acceptable tolerability and seizure control on the same daily dose of BRV (no lower than the minimum specified dose) for 7 ± 2 days of the Up-Titration Period. For subjects who continue in this study until it ends, the Evaluation Period will extend from the EV until the final evaluation visit (Final Visit, FV). For subjects who prematurely discontinue the study, the Evaluation Period will last from the EV until the Early Discontinuation Visit (EDV), followed by a maximum 4-week Down-Titration Period, a 2-week Safety (Drug-Free) Period, and a final Safety Visit (SV). Subjects already enrolled in N01266 may participate in EP0065 (an intravenous [iv] BRV study for pediatric subjects), if eligible, and then resume participation in N01266.

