4.8 Examination of subgroups

Selected summaries will be provided for the following subgroups as specified within each of the following sections:

- Previous pediatric BRV study experience, labelled with “Cohort” (LTFU subjects overall and by core study, DE subjects)
- Age group (≥ 1 month to < 2 years of age (28 days to 23 months), ≥ 2 to < 4 years of age, ≥ 4 to < 12 years of age, ≥ 12 to < 17 years of age)
- Seizure category (POS, PGS*, Typical Absence, PGS) as defined in Section 3.10.3.
- Geographical region (North America, Latin America, Western Europe, Eastern Europe, Asia/Pacific/Other)

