5 STUDY POPULATION CHARACTERISTICS

5.1 Subject disposition

An overall summary of disposition will be provided for enrolled subjects, in SS and FAS, and in SS by subgroups, separately. The following will be summarized:

- The number of enrolled subjects
- The number of screen failures (DE subjects only)
- The number of subjects in the SS (applicable for enrolled subjects table only)
- The number of subjects excluded from the SS (applicable for enrolled subjects table only)
- The number of subjects in the FAS (applicable for enrolled subjects table only)
- The number of subjects entering the Up-Titration, Evaluation, Down-Titration Period
- The number of subjects completing the Up-Titration and entering the Evaluation
- The number of subjects completing the study
- The number of subjects ongoing in the study (only applicable before final data base lock)
- The overall number of subjects discontinuing and the number of subjects discontinuing by primary reason for discontinuation. If the subject discontinued the study and the termination CRF is not available, the reason for discontinuation will be reported as “UNKNOWN”.

Overall subject disposition will also be summarized by cohort (LTFU vs. DE), and geographical region, by seizure category and by core study for the SS.

The number of subjects by cohort and geographical region will be summarized for the SS.

The number of subjects in each analysis set (Enrolled Subjects, SS and FAS) will be presented by investigator and cohort, including the dates of the first subject in (date of earliest EV for the N01266 study) and the last subject out (date of final scheduled or UV). The table will be presented overall and by region.

The number of subjects and Kaplan-Meier estimates of the percentage of subjects completing 3, 6, 12, 24, 36, 48 and 60 months of treatment with BRV in the N01266 study will be provided.

This analysis will be based on duration of exposure to BRV as defined in Section 3.2.7. Subjects who have permanently discontinued will be analyzed as events on the final day of treatment with BRV; subjects who complete the study will be censored on the final day of treatment with BRV.

Subjects who transferred sites will be summarized according to their original site.

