8.4 Vital signs, physical findings, and other observations related to safety

8.4.1 Vital signs

Vital signs, including measurements of blood pressure, supine or sitting pulse rate, and body temperature, are assessed after 5 minutes of rest at the ScrV, TV(s), and EV, MEV, FEV, YEV, FV, and at the EDV, Down-Titration Visit (DTV), and the SV in the case of early discontinuation. For LTFU subjects, at the EV, vital sign data will be obtained from the final visit of the core study (if available) and should not be recorded in the eCRF for N01266. If not available, vital signs data will be recorded within N01266 as for DE subjects.

Observed values and change from Baseline value for SBP, DBP, and pulse rate will be summarized for Baseline, EV, each visit during the Evaluation Period for which vital signs or body weight were assessed, EDV, Last Value on Treatment, FV, the Down-Titration Visit (DTV), and the Safety Visit (if available). This summary will be repeated separately for data collected during the Up-Titration visits for DE subjects.

The PCST criteria are based on FDA Division of Neuropharmacological Drug Products guidelines with some UCB-defined additions.

The number and percentage of subjects with any post-Baseline PCST value, any PCST low value, and any PCST high value will be summarized for SBP, DBP, pulse rate, and body weight. This summary will consider all assessments after the first dose of BRV and prior to or on the date of the final dose of BRV (excluding Up-Titration Assessments for DE Subjects). Percentages will be relative to the number of subjects with a post-Baseline assessment. This summary will be repeated for the Up-Titration Period for DE Subjects.

Additionally, the PCST table will be provided stratified by visit for all visits during Evaluation Period. Percentages will be relative to the number of subjects with a value at the corresponding visit.

A subject number table will be provided that identifies subjects with a clinically significant finding after the first dose of BRV for each type of vital sign abnormality.

All vital signs will be provided in subject data listings.

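### The age bands for abnormal laboratory values and vital signs leave some assessed ages without a limit but keep them in the denominators, and the weight rule from 17 years can count ordinary growth as an abnormality

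*SAP*

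**What the plan says.** **Who is assessed, and at what ages.** SAP section 2 describes a study for "pediatric subjects ≥ 1 month to <17 years of age who have completed other pediatric BRV studies", plus directly enrolled (DE) subjects aged 4 to under 17. It adds: "Subjects will receive BRV treatment in this study for at least 3 years", subject to several other end points, whichever comes first. Section 5.1 plans retention estimates at "3, 6, 12, 24, 36, 48 and 60 months of treatment with BRV".

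**Limits.** In Appendix 12.3 the top band for pulse, systolic and diastolic pressure is 12 to under 17 years. Body weight alone has a further row from 17. In Appendix 12.1 alkaline phosphatase stops at 17, serum creatinine at 16, and ALT, GGT, haemoglobin and haematocrit at 18. ALT and serum creatinine start at 1 year. White cells, red cells and AST are open at the top.

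**Weight.** Below 17 the rule is a growth-curve centile, "based on gender and the age of subject on date of weight assessment". From 17 it is "A decrease/increase from Baseline of" 10% or more. Under section 3.3, Baseline weight is the last pre-dose value for DE subjects. For subjects from a core study (LTFU) it is the last value up to the first brivaracetam dose in that core study.

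**Denominators.** Section 8.4.1 says of the by-visit vital-sign table: "Percentages will be relative to the number of subjects with a value at the corresponding visit". Its overall table uses all subjects with a post-Baseline assessment. Section 8.3 uses all subjects with an on-treatment assessment. None of these excludes values at ages without a limit.

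**The concern.** A subject with no applicable limit can never enter the numerator but stays in the denominator, so the table treats an unclassifiable value as a normal one. As the cohort ages past 17, the by-visit pulse and blood pressure percentages in the oldest group fall for a reason unrelated to the drug. Weight moves the other way: after years of adolescent growth, comparison with a fixed earlier weight can turn normal development into a counted abnormality. A reader of the long-term safety tables could take either pattern for a treatment effect. The weight row from 17 shows that assessments at those ages are expected, so the other rows of Appendix 12.3 do not match the plan's own age range.

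**Working it through.** **Step 1: coverage.** Each band was read as an interval and compared with ages from 1 month upward, taking age at assessment.

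| Parameter | Ages without a limit |
|---|---|
| Pulse, SBP, DBP | from 17 years |
| Alkaline phosphatase | from 17 years |
| Serum creatinine | under 1 year; from 16 years |
| ALT | under 1 year; from 18 years |
| GGT, haemoglobin, haematocrit | from 18 years |
| Creatinine clearance, AST, bilirubin, white cells, red cells, weight | none |

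Serum creatinine fails even within the entry range, since a 16-year-old is eligible and has no limit at any visit.

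**Step 2: share uncovered for pulse and blood pressure.** The SAP gives no entry-age distribution, so uniform entry is assumed.
- Oldest group, 12 to under 17: those entering at 14 or older pass 17 within 3 years, so (17 − 14)/(17 − 12) = 3/5 = 60%. With the SAP's 30-day months, Month 36 is 1,080/365.25 = 2.96 years, giving 2.96/5 = 59%.
- All entrants, 1 month to under 17: 3/16.92 = 18% within 3 years and 5/16.92 = 30% within 5 years.

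If the abnormality rate among covered subjects at a visit is p and the uncovered share is u, the table prints p × (1 − u). In the oldest group at Month 36 that is p × (1 − 0.60) = 0.40p.

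**Step 3: infants.** The laboratory table counts any post-Baseline PCST value over the period. A child entering under 1 year is covered for ALT and creatinine from the first birthday, so the loss is confined to earlier values.

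**Step 4: weight from 17.** The yearly gain that reaches +10% after T years is 1.10^(1/T) − 1: 4.9% for T = 2, 3.2% for T = 3 and 1.9% for T = 5. The SAP gives no growth figures, so for an assumed Baseline weight W and gain g the time to the flag is 0.10 × W/g.
- W = 40 kg, g = 2 to 4 kg per year: 2.0 to 1.0 years.
- W = 50 kg, same gains: 2.5 to 1.25 years.
- W = 60 kg, same gains: 3.0 to 1.5 years.
- At g = 1 kg per year the 3-year changes are 3/40 = 7.5%, 3/50 = 6.0% and 3/60 = 5.0%, so there is no flag.

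**The case against.** The strongest reply is that little is hidden and nothing primary changes. Section 2.2.1 makes treatment-emergent adverse events, including serious ones, the primary variables. Laboratory tests, vital signs and weight are listed under other variables in 2.2.3, and all summaries are descriptive. Observed values and changes from Baseline are tabulated by visit for pulse, blood pressure and the laboratory parameters, and all values are listed. In the overall vital-sign table nearly every subject has some value before 17 and can be flagged, so the dilution lies mainly in the by-visit table. All of this stands, and it limits the severity.

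A reader might infer that infants have no usable hepatic or renal criterion. The document does not support that. AST, GGT and bilirubin limits apply to infants, creatinine clearance applies at all ages, and ALT and creatinine limits apply from the first birthday.

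A reader might also infer that weight abnormality rates must approach 100%. That does not follow. Slow growers and subjects assessed soon after entering just under 17 would not be flagged, and younger subjects remain under the centile rule. Section 8.4.1 also separates low from high values, so weight loss stays readable; growth distorts the high and any-value counts.

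Finally, banding on entry age would remove the pulse and blood pressure gap, since nobody enters at 17. Only the weight row says which age applies. That reading would also leave children entering under 1 year without an ALT limit throughout follow-up.

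**Conclusion.** The point holds. The bands do not span the ages the plan enrols and follows, and the denominators turn that gap into apparent normality. The main effect is on the by-visit pulse and blood pressure rates at late visits in the oldest group, which would print at about 0.4 of the rate among covered subjects at Month 36. That figure assumes uniform entry ages over 12 to under 17, banding on age at assessment, and subjects still on study; an earlier listed end point would reduce it. A smaller effect is that ALT and creatinine PCST values before the first birthday are lost, as are creatinine values from 16. The weight rule from 17 can count ordinary growth, and 3.2% per year over three years suffices, but how often it does so depends on growth that the SAP does not describe. Should-fix: the affected tables are descriptive and outside the primary variables, but they would be wrong as specified.

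**What to change.** - In sections 8.3 and 8.4.1, restrict each PCST numerator and denominator, overall and by visit, to subjects with at least one value at an age for which a criterion exists. Show the number not evaluable beside it.
- State in section 3.9 or the appendices that age at assessment governs banding for every parameter.
- Have the sponsor's safety physician reconcile the closed and missing bands in Appendices 12.1 and 12.3 with the enrolled and followed age range. The limits are for that role to set.
- From 17 years, replace the comparison with Baseline weight by a growth-adjusted reference, for example the age- and sex-centile rule as far as the growth curves extend. Alternatively, report gain and loss separately and keep gain out of the any-abnormality count.

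The cost is a sentence in each of two or three sections, edits to two appendix tables and a change to the programming look-up before database lock. No new data are needed.
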